Setting: The neonatal unit at UAB is one of the largest neonatal academic centers in the United States. We have admitted more than 200 very preterm infants over the past 2 years. This large numbers of very preterm infants admitted makes our unit the ideal environment to conduct comparative effectiveness trials.

Participants: Very preterm infants with gestational ages between 28 and 32 weeks of gestation at the time of admission to our neonatal unit will be eligible for this trial. Gastrointestinal or neurologic malformations, and terminal illness requiring limited or withheld support will be exclusion criteria.

[figure not shown]
Randomization, allocation concealment, and masking: After receiving approval by the Institutional Review Board (IRB) at UAB to conduct this trial, research nurses and investigators will obtain written parental consent before randomization. We will randomize study participants using computer generated random-block sequences and numbered, opaque, sealed envelopes that will be opened in sequential order. Twin infants will be randomized individually. The intervention will not be masked.

Intervention: Infants randomly assigned to the intervention group will have the information about infant body composition known to the clinicians caring for them (including reference data). The use of this patient-specific information about nutritional status will assist clinicians to optimize nutrition using feeding guidelines that will be provided. Infants randomly assigned to the control group will also undergo serial measurements of body composition, but this information will not be available to the clinicians.

Primary and secondary outcomes: The primary outcome will be %BF estimated by air displacement plethysmography at 3 months of age. Secondary outcomes will include %BF and fat-free mass (FFM) at 36 weeks of postmenstrual age (PMA) or hospital discharge (whichever occurs first), postnatal growth restriction (below 10th percentile) at 36 weeks PMA or discharge, weight gain (g/kg/d) from birth to the end of the intervention, anthropometric measures at time of hospital discharge (weight, head circumference, and length), weight gain (g/kg/d) from hospital discharge to 3 months of age, anthropometric measures at 3 months of age (weight, head circumference, and length), and blood pressure values at 3 months of age.

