Assessment of infant body composition: Serial assessments of infant body composition with air displacement plethysmography in very preterm infants using the PeaPod® (Life Measurement Instruments, Concord, CA)³² will occur in the first 14 days after birth (baseline measure), at 32 weeks PMA, at 36 weeks PMA or hospital discharge (whichever occurs first), and at 3 months of age [Figure 2]. The PeaPod® and the neonatal unit are located in the same building. During hospitalization, nursery staff and parents, if present, will transport the infant to the exam room where the PeaPod® is located. In the exam room, nursery staff will undress the infant, place the snug cap, and transfer the infant to the PeaPod® when ready for weighing and scanning. The infant will wear only a cap on his/her head and will lie inside the scanner for approximately 2-3 minutes to estimate total fat and fat-free mass according to body weight and volume⁴⁷. The infant will breathe the normal air in the room and will be able to see and hear his/her parents. Equipment for respiratory support or monitoring will not be used during the assessment to avoid unnecessary recalibration of the PeaPod®. For assessment of body composition at 3 months of age, a follow-up visit will be scheduled prior to discharge from the hospital. The 3-month visit will also include a brief questionnaire about feeding practices at home and blood pressure measurements. The study coordinator will mail a reminder letter approximately 2 weeks prior to the date of the visit and will call the caregiver to remind them on the day prior to their scheduled appointment. Infants and a caregiver will return to the hospital to repeat the body composition assessment. A trained technician from the Nutrition Obesity Research Center (which owns and manages the PeaPod®) will operate it.

Figure 2. Serial assessment of body fat accrual in very preterm infants*

* Traditional growth chart report (A) and body fat accrual report (B) of a preterm infant born at 29 weeks of gestation and monitored from birth to 36 weeks PMA

Control or monitoring of co-interventions: Clinical care and decisions about enteral nutrition will be conducted at the discretion of the attending physician.

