Study specimens. Because several experiments suggest that changes in gut microbiota can influence obesity⁴⁸, we will obtain written informed consent from the parent(s) to collect 2 stool samples, 1 stool sample before hospital discharge and 1 stool sample at the 3-month follow-up visit for possible use in future studies. Similarly, consent from the parent(s) will be obtained to collect a serum sample and measure biomarkers of anabolism and growth prior to hospital discharge.

Statistical Analysis Plan. This trial will record core data on nutrition as recommended by consensus groups⁴⁹. For analysis of the primary outcome, an unadjusted T-test comparison of the mean %BF between control and intervention groups will be performed assuming a normal distribution of this variable⁵⁰. In consideration of relevant biological variables, a pre-specified adjusted analysis for demographic and nutritional characteristics will be conducted to improve precision in treatment comparisons and remove variability associated with these covariates^{51,52}. A similar approach will be used for secondary outcomes. Descriptive data will be expressed as the mean (SD) or number (percentage) of observations. The primary statistical analyses will be performed on an intention-to-treat basis⁴⁹ with SAS software.

Sample Size and Power Estimates. At our institution, the mean and SD of %BF in preterm infants at time of discharge is 15 and 3.6, respectively (unpublished data). Therefore, to detect a 3-point difference in %BF between groups with SD of 3.6, 0.05 level of significance, and 80% power for a T-test that compares means from two independent samples, a sample size of 46 patients will be necessary in this superiority trial. Anticipating that approximately 10% of study participants will be lost to follow-up for assessment of the primary outcome at 3 months of age, 2 patients will be added to each group and the sample size will be increased to 50. We will include a total of 25 patients in each group (n=50).

Potential Problems

Enrollment rates: An average of 7 study participants per month were enrolled in a recently completed trial that assessed body composition of very preterm infants at our institution (unpublished data). To define a timeline for patient enrollment in this trial, we assumed that 50% of parents will refuse participation.

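### The primary analysis leaves out the baseline %BF scan scheduled in both arms; adjusting for it could add power, by an amount that depends on a correlation the plan does not give

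*Combined protocol and SAP*

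**What the plan says.** - **Primary test** (Statistical Analysis Plan): "For analysis of the primary outcome, an unadjusted T-test comparison of the mean %BF between control and intervention groups will be performed".
- **Scan schedule** (Assessment of infant body composition): air-displacement plethysmography scans "will occur in the first 14 days after birth (baseline measure), at 32 weeks PMA, at 36 weeks PMA or hospital discharge (whichever occurs first". The last scan, at 3 months, supplies the primary outcome.
- **Control arm** (Intervention): "Infants randomly assigned to the control group will also undergo serial measurements of body composition, but this information will not be available to the clinicians".
- **Supporting analysis** (Statistical Analysis Plan): "a pre-specified adjusted analysis for demographic and nutritional characteristics will be conducted to improve precision in treatment comparisons". It gives no covariate list and no model. Baseline %BF is not named as a covariate there or elsewhere.
- **Sample size** (Sample Size and Power Estimates): 46 infants "to detect a 3-point difference in %BF between groups with SD of 3.6, 0.05 level of significance, and 80% power for a T-test", raised to 50 for about 10% loss to follow-up. The SD comes from an earlier time point: "the mean and SD of %BF in preterm infants at time of discharge is 15 and 3.6, respectively (unpublished data".

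**The concern.** The trial schedules its own outcome variable, on the same device, near the start of follow-up in both arms. If infants who begin with more fat tend to have more at 3 months, an unadjusted comparison leaves that predictable variation in the error term. A model that includes the baseline value would remove it. The same model would also correct the estimate for whatever baseline difference arises by chance between two arms of 22 or 23 infants.

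This matters more in a small trial with little power to spare. The plan already gives precision as the reason for its supporting adjusted analysis, but it does not name the one early measurement on the outcome's own scale, and it gives no reason for leaving that value out of the primary test.

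**Working it through.** **Inputs.** From Sample Size and Power Estimates: difference 3, SD 3.6, alpha 0.05, power 80%, 46 evaluable, 50 randomised, about 10% loss. The plan does not say whether alpha is one- or two-sided; two-sided reproduces its figure and one-sided (36) does not. The correlation rho between baseline and 3-month %BF is an assumption, shown over a range. Infants are treated as independent.

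**1. The plan's own figure.** Normal approximation: n per arm = 2 × (1.960 + 0.842)² × 3.6² / 3² = 22.6, so 23 per arm and 46 in total. This matches. Using the t distribution, 24 per arm (48) are needed, and 23 per arm give 78.9% power.

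**2. Unadjusted test at the expected follow-up.** 50 × 0.90 = 45 infants, taken as 23 and 22.
- Standard error = 3.6 × √(1/23 + 1/22) = 3.6 × 0.298 = 1.074.
- Noncentrality = 3 / 1.074 = 2.794, on 43 degrees of freedom.
- Power = 78.0%. The 95% CI half-width = 2.017 × 1.074 = 2.17 points.

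**3. ANCOVA on baseline %BF alone.** The residual SD is 3.6 × √(1 − rho²). One degree of freedom is lost, leaving 42. The variance is multiplied by 1 + 1/(45 − 4) = 1.024 to allow for chance imbalance in the covariate. For rho 0.5, the residual SD is 3.118, the standard error is 3.118 × 0.298 × √1.024 = 0.941, and the noncentrality is 3 / 0.941 = 3.19.

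| rho | residual SD | power | change from 78.0% | 95% CI half-width |
|---|---|---|---|---|
| 0 | 3.600 | 77.0% | −1.0 | 2.19 |
| 0.2 | 3.527 | 78.6% | +0.6 | 2.15 |
| 0.3 | 3.434 | 80.7% | +2.7 | 2.09 |
| 0.4 | 3.299 | 83.7% | +5.7 | 2.01 |
| 0.5 | 3.118 | 87.6% | +9.6 | 1.90 |
| 0.6 | 2.880 | 92.1% | +14.1 | 1.75 |

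Break-even is at rho of about 0.16. A 5-point gain needs rho of about 0.38.

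**4. Further covariates.** With k covariates the variance factor is 1 + k/(45 − k − 3), on 43 − k degrees of freedom. If age at scan and a missing-value indicator were added and explained nothing (k = 3), break-even would rise to rho of about 0.27, and rho 0.2 would then mean a loss of power.

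**5. Chance imbalance.** At rho 0.5, a baseline difference of one standard error (0.298 SD) moves the unadjusted estimate by 0.5 × 3.6 × 0.298 = 0.54 points, which is 18% of the 3-point target.

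**The case against.** The strongest reply is that nothing here is wrong. The t-test is valid under randomisation and is the test on which the sample size was built. The Generalizability paragraph accepts limited precision in a pilot. That stands. The 0.54-point shift is not bias either, because the t-test's standard error already covers it.

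Three stronger readings are tempting, and the documents do not support them.

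- **That power is certainly lost.** No correlation is given, and it could be low. The Significance section says that body composition at term-equivalent age, unlike at 3 months, does not correlate strongly with the value at 4 years. It also reports %BF at birth rising with gestational age (6% at 30 weeks, 9.5% at 37 weeks), so part of an early scan may reflect maturity. Below rho of about 0.16 there is no gain.
- **That the supporting adjusted analysis excludes baseline %BF.** Its covariates are unnamed. The Intervention paragraph describes body-composition results as information on nutritional status, so the nutritional class could include the baseline scan. What can fairly be said is that the plan does not specify it.
- **That adjustment costs nothing.** Scans are done without respiratory-support equipment, so some baseline scans may be missed and a rule is needed. The plan also does not say whether the scan precedes randomisation, and the trial is unmasked. Discarding scans made after a report could be acted on would make matters worse. Control results are withheld, so that rule could apply only in the intervention arm and would make missingness depend on arm.

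**Conclusion.** The point holds as a matter of efficiency. Baseline %BF is scheduled in both arms, the primary test leaves it out, and the plan nowhere names it as a covariate. With 45 evaluable infants the balance favours adjustment: a loss of about 1 point of power at worst, against gains of about 3 points at rho 0.3, 10 at 0.5 and 14 at 0.6. Which of these applies cannot be settled from the documents.

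The figures rest on the plan's 3-point difference, on an SD of 3.6 measured at discharge and carried to 3 months, on two-sided 0.05, on a 23/22 split, and on a single covariate related linearly to the outcome. A reader should not infer that the planned t-test is biased, or that a stated amount of power is being thrown away.

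**What to change.** In the Statistical Analysis Plan section, before the data are analysed:

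1. Make the primary analysis a linear model (ANCOVA) of 3-month %BF on arm and baseline %BF. Keep the unadjusted t-test as a supporting analysis.
2. Define the baseline value by one rule applied identically in both arms: the infant's first scan, within 14 days of birth, regardless of when any report was issued.
3. Fill a missing baseline value with the overall mean across both arms, so that every infant with a 3-month scan stays in the analysis.
4. Treat age at scan as optional, since each added covariate raises the break-even correlation.
5. Use the same adjustment for %BF at 36 weeks PMA or discharge, and baseline FFM for FFM at that time.
6. State the correlation assumed between baseline and 3-month %BF.

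The cost is a few sentences, one degree of freedom, about 1 point of power if rho is near zero, and a simple rule for missing scans. No new measurement is needed.

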Sample size: A negative outcome (i.e. %BF) was selected as the primary efficacy end point of this trial. We used our own institutional data to calculate the sample size for this trial and estimated that a 3% absolute difference was clinically meaningful because the average difference between term and preterm infants is 3%.⁶

Follow-up: We estimated that follow-up rates at 3 months of age will be higher than our follow-up rates at 2 years of age for extremely preterm infants (approximately 80% at our institution). Follow-up at 3 months of age to assess infant body composition will allow comparison of our results with reference data in term infants.

Generalizability: Given the pilot nature of this trial, we will focus on minimizing systematic errors in the trial to improve accuracy of our results and increase internal validity. It is expected that the precision of our estimates and the external validity of our results will be affected by our small sample size.

Specific Aim 2 will test the hypothesis that serial assessment of infant body composition slows weight gain following hospital discharge and attenuates health disparities in body fat accrual at 3 months of age.

Overview and preliminary data: Aim 2 will be a secondary analysis of our pilot randomized trial. In a prospective study of body composition, we corroborated that racial/ethnic minorities have higher in-hospital growth rates than white infants (unpublished data).

Inclusion criteria, exclusion criteria, and outcome: Demographic and nutritional data from infants who participated in the pilot trial will be used for this analysis. Infants with missing follow-up data will be excluded. %BF at 3 months of age will be the dependent variable in the primary analysis.

Statistical analysis: In this analysis, race/ethnicity will be entered as a dichotomous variable: white (reference group) and black or Hispanic. To examine the association between weight gain at 2 different time points (before and after hospital discharge) and body fat accrual at 3 months of age within each racial/ethnic group, we will use multivariable regression models. Subsequently, to quantify the degree to which weight gain explains racial/ethnic disparities in body fat accrual, we will employ a decomposition analysis which will help us determine if changes in weight gain after serial monitoring of body fat accrual reduces differences (i.e. observed and predicted) in body fat accrual between minority and white infants⁷.

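### The intention-to-treat label does not say how infants without a 3-month scan are analysed, and the primary t-test leaves the earlier %BF scans unused

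*Combined protocol and SAP*

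**What the plan says.** The Statistical Analysis Plan section says that for the primary outcome "an unadjusted T-test comparison of the mean %BF between control and intervention groups will be performed", and adds that "The primary statistical analyses will be performed on an intention-to-treat basis". The endpoint is a single-visit measurement: "The primary outcome will be %BF estimated by air displacement plethysmography at 3 months of age".

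The Sample Size and Power Estimates section expects about 10% of infants to have no 3-month measurement and responds by adding two infants per group. No imputation, likelihood-based model, missing-data assumption or missing-data sensitivity analysis is described anywhere in the document.

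Earlier scans are planned. Under Assessment of infant body composition they "will occur in the first 14 days after birth (baseline measure), at 32 weeks PMA, at 36 weeks PMA or hospital discharge". Under Intervention, "Infants randomly assigned to the control group will also undergo serial measurements of body composition", so these data will exist in both arms. The plan also promises that "a pre-specified adjusted analysis for demographic and nutritional characteristics will be conducted to improve precision in treatment comparisons", but earlier %BF is not named among the covariates.

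For Aim 2, which has the same 3-month outcome, the rule is explicit: "Infants with missing follow-up data will be excluded".

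**The concern.** A two-sample t-test has no place for an infant without a 3-month value. The primary analysis is therefore a completers analysis in effect, although the plan does not say so. Adding two infants per group protects power but does nothing about bias.

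Loss could plausibly be uneven. The trial is not masked, clinicians receive %BF information in one arm only, and the 3-month scan requires the family to come back to the hospital. If return depends on growth already seen before discharge, and does so differently by arm, the difference among completers is not the difference among all randomised infants. The trial will hold scans that bear on this, and the primary test ignores them.

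The same scans could sharpen the comparison, which matters in a trial of 50 infants.

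**Working it through.** **Inputs from the plan.** Target difference 3 points, SD 3.6, level 0.05, power 80%, 46 evaluable infants, 50 randomised 1:1, loss about 10%. Sidedness is not stated; two-sided is assumed because it reproduces the plan's number (one-sided gives 36).

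**Assumptions.** The documents give neither the correlation between earlier and 3-month %BF nor any loss mechanism, so ranges are shown. The SD is taken as 3.6 at each visit.

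**1. The plan's own figure.** n per arm = 2 × (3.6 × (1.960 + 0.842) / 3)² = 22.6, rounded up to 23, so 46 in total. This matches.

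**2. Infants left in the t-test.** 50 × 0.90 = 45. SE = 3.6 × √(4/45) = 1.07. Power is 79.8% by the normal approximation and 78.0% by the exact t calculation.

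**3. Bias under random loss.** Zero. The cost is precision only.

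**4. Bias under one-arm dependent loss.** Let 16% be lost in the intervention arm and 5% in control (average 10.5%). Intervention loss follows a logistic curve in 36-week %BF; control loss is unrelated to it. With equal SDs, bias = correlation × 3.6 × m, where m is the mean 36-week %BF of retained intervention infants, in SD units, relative to their whole arm.

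| Logistic slope per SD | m | Lost minus retained, 36-week %BF | Bias, correlation 0.4 | Bias, correlation 0.6 |
|---|---|---|---|---|
| 0.5 | −0.077 | 1.7 points | −0.11 | −0.17 |
| 1.5 | −0.186 | 4.2 points | −0.27 | −0.40 |

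For example, 0.6 × 3.6 × (−0.186) = −0.40. The sign is negative because fatter intervention infants leave, which exaggerates the benefit.

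A second simulation reversed the pattern: fatter control infants and leaner intervention infants were lost, at a slope of 1 per SD and about 13% average loss. The completers estimate then moved towards zero by 0.25 to 0.58 points for correlations of 0.3 to 0.7. A likelihood estimate using the pre-discharge scan stayed within about 0.02 of the true effect in that simulation, as it should when loss depends only on a scan in the model.

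**5. Where the precision comes from.**
- *Recovering lost infants.* The variance reduction is roughly loss fraction × correlation². At 10% loss and correlation 0.4 to 0.6 this is 0.10 × 0.16 = 1.6% to 0.10 × 0.36 = 3.6%.
- *Using baseline %BF.* The residual SD is 3.6 × √(1 − correlation²). At 0.3 it is 3.43; at 0.5 it is 3.12. With 45 evaluable infants, exact-t power rises from 78.0% to 81.7% and 88.4% respectively (ignoring the one degree of freedom spent).

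**The case against.** The strongest reply is that the bias is assumed, not shown. No passage says that loss will differ by arm or depend on %BF. The plan schedules the 3-month visit before discharge, mails a reminder and telephones the day before, and it expects follow-up better than about 80%. The top of the 0.1 to 0.4 range needs lost intervention infants to average about 4.2 points more 36-week %BF than retained ones, which exceeds the target effect. At the milder slope the bias is 0.11 to 0.17 points against an SE of 1.07. All of this stands. A reader might infer that the t-test will be biased here; the documents support only a conditional risk. Scenarios with loss well above 20% give larger figures but fall outside the plan's own expectation.

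The near-unbiasedness of the likelihood model is also conditional. If return depends on events at home or growth after discharge, in-hospital scans will not correct for it.

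A reader might also infer that Aim 2 contradicts the intention-to-treat sentence. It does not: that sentence covers the primary analyses, and Aim 2 is declared a secondary analysis with its exclusion stated openly. Nor should the loss of precision be blamed mainly on the missing infants; step 5 shows that baseline %BF matters more.

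Finally, a model with all four visits and an unstructured covariance would fit the schedule poorly. For infants born near 32 weeks, the baseline scan (up to day 14) and the 32-week scan coincide or reverse order. With 50 infants, a small-sample correction is also needed. Both points are accepted and shape the fix.

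**Conclusion.** The point holds as an inexpensive improvement. The plan uses an intention-to-treat label without saying how about 5 of 50 randomised infants are to be handled. Their exclusion from the primary analysis is implied by the test, not written down; only Aim 2 states an exclusion. Analysing infants in their assigned arm is consistent with the label, but it does not settle the missing values.

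The gain in power to about 82–88% rests on an assumed baseline correlation of 0.3 to 0.5. The bias range rests on the assumed unequal loss and its assumed dependence on 36-week %BF. Neither is a prediction. The case for acting is that the scans are already planned in both arms, and that a method named in advance avoids a choice made after the data are seen.

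**What to change.** - **Primary analysis.** Estimate the arm difference in %BF at 3 months from a likelihood-based repeated-measures model of the baseline, 36-week/discharge and 3-month scans, with a common baseline mean, arm-by-visit effects and the Kenward-Roger correction. Include every randomised infant with any of these scans, in the assigned arm. Leave the 32-week scan out of the visit structure because it overlaps baseline for infants born near 32 weeks.
- **Baseline timing.** State when the baseline scan falls relative to randomisation, since the common-mean assumption requires that it precede any effect of the intervention.
- **Supporting analysis.** Keep the unadjusted t-test and describe it as an analysis of infants with a 3-month scan.
- **Sensitivity analysis.** Add one that shifts the missing 3-month values separately by arm, to show how far they would have to differ to change the conclusion. Report loss by arm.
- **Aim 2.** Keep the stated exclusion and report it as a completers analysis. Use imputation at most as a sensitivity analysis, because post-discharge weight gain, a key predictor, will usually be missing for the same infants.

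The cost is revised wording and modest SAS programming, with no new data. The downside is a slightly more complex primary model that assumes loss depends on observed data, which is why the sensitivity analysis is needed.

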Specific Aim 1: To test the hypothesis that provision of serial body fat accrual reports during hospitalization will enable personalized dietary interventions and reduce adiposity at 3 months of age in very preterm infants. We chose %BF at 3 months of age as the primary outcome of the trial because at this age: 1) body fat accrual can be measured with non-invasive methods¹⁰; 2) loss to follow-up rates are low⁹; 3) physical activity and other risk factors for obesity are less likely⁷; and 4) correlation with body fat accrual at preschool age is strong⁹. We selected very preterm infants as the ideal population to study the risk of obesity in preterm infants because they: 1) experience a high risk for adverse health outcomes^{3,5}; 2) usually do not require supplemental oxygen after postnatal day 7; and 3) receive strictly controlled diets for more than 30 days from birth to hospital discharge. With our improved understanding of the interaction between infant weight, body fat accrual, and dietary interventions, we plan to examine whether the provision of body fat accrual reports to clinicians and parents will impact infant weight gain and body fat accrual¹¹.

Specific Aim 2: To test the hypothesis that serial assessment of infant body composition attenuates health disparities in body fat accrual at 3 months of age by slowing weight gain following hospital discharge. The rationale for this aim is: 1) rapid weight gain during early infancy is highly prevalent among racial/ethnic minorities^{12,13}; and 2) adjustment for rapid weight gain attenuates disparities in childhood obesity between racial/ethnic minorities and white infants^{7,12}. We hypothesize that our intervention focused on personalized dietary interventions based on changes in infant body composition will reduce rapid weight gain and attenuate health disparities in body fat accrual.

RESEARCH STRATEGY

SIGNIFICANCE

Rapid weight gain increases the risk of metabolic reprogramming in preterm infants. For many years, the high prevalence of postnatal growth failure (weight below the 10th percentile for expected intrauterine growth) in the preterm population made weight the most important outcome of growth among preterm infants. Similarly, the association between rapid weight gain and improved neurodevelopment led clinicians to assume that slow weight gain was “inadequate growth” and that high-calorie diets to promote rapid weight gain were needed.

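### Aim 2 hypothesises that the intervention narrows the minority-white gap in body fat, but no analysis compares that gap between the randomised arms

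*Combined protocol and SAP*

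**What the plan says.** The opening statement of Specific Aim 2 proposes that "serial assessment of infant body composition attenuates health disparities in body fat accrual at 3 months of age by slowing weight gain" after discharge. The Approach section repeats it: serial assessment "slows weight gain following hospital discharge and attenuates health disparities in body fat accrual at 3 months of age". Both are claims about an effect of the intervention, and Aim 2 is presented as a secondary analysis of the randomised trial.

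The Statistical analysis paragraph under Specific Aim 2 sets out these elements:

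- Race/ethnicity is coded in two levels, "white (reference group) and black or Hispanic".
- The association of weight gain (before and after discharge) with 3-month body fat is examined "within each racial/ethnic group, we will use multivariable regression models".
- A decomposition follows, "to quantify the degree to which weight gain explains racial/ethnic disparities in body fat accrual", which is meant to "determine if changes in weight gain after serial monitoring of body fat accrual reduces differences (i.e. observed and predicted) in body fat accrual". The difference in question is the minority-white one.

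Elsewhere, the Primary and secondary outcomes paragraph lists "weight gain (g/kg/d) from hospital discharge to 3 months of age", and the Statistical Analysis Plan paragraph compares %BF between arms by t-test and treats secondary outcomes similarly. It also plans an adjusted analysis for demographic and nutritional characteristics, with precision as the stated purpose.

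**The concern.** The Aim 2 hypothesis has two parts. The first, slower weight gain after discharge, does get an overall comparison between arms, because that weight gain is a secondary outcome. The second, a smaller minority-white gap, does not. Answering it requires the gap in the intervention arm minus the gap in the control arm. Neither the regressions nor the decomposition defines that difference. The plan also does not say whether the arms are pooled, which covariates enter the models, or what the observed and predicted differences compare.

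The share of the racial/ethnic gap explained by weight gain is an observational quantity. It describes the proposed pathway, but it cannot replace the randomised comparison. Followed as written, the plan can leave one of its stated hypotheses unanswered. It also leaves room to choose among pooled, by-arm and arm-adjusted readings after the data are seen.

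**Working it through.** **1. The plan's own figure.** The documents give no sample size, power or effect size for Aim 2. The only figure to reproduce is the primary one in Sample Size and Power Estimates (difference 3, SD 3.6, alpha 0.05, power 80%):

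n per arm = 2 × (1.960 + 0.842)² × 3.6² / 3² = 22.6, so 23 per arm and 46 in total. This matches the plan.

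**2. What pooled output can show (assumed inputs).** Let weight gain be in arbitrary units with a slope of 1.0 on %BF, with 1:1 arms and the same racial/ethnic mix in each. Then:

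- pooled gap = (control gap + intervention gap) / 2
- explained share = slope × pooled weight-gain gap / pooled gap
- interaction = intervention gap − control gap

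*All of the gap acts through weight gain:*

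| Gap, control/intervention | Pooled gap | Explained share | Interaction |
|---|---|---|---|
| 2/0 | (2+0)/2 = 1 | 1×1/1 = 1 | −2 |
| 1/1 | (1+1)/2 = 1 | 1×1/1 = 1 | 0 |
| 0/2 | (0+2)/2 = 1 | 1×1/1 = 1 | +2 |

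A simulation of 400,000 infants per scenario agreed: pooled gaps 1.01, 0.99 and 1.01; shares 0.99, 1.01 and 0.99; interactions −2.00, 0.03 and 2.02.

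*Half of the gap change bypasses weight gain:* the pooled weight-gain gaps become (2+1)/2 = 1.5, (1+1)/2 = 1 and (0+1)/2 = 0.5. The pooled gap stays at 1, so the shares are 1.5, 1.0 and 0.5 (simulated 1.57, 1.01 and 0.51; the first depends on which slope is used). The shares now differ, but they still do not identify the effect. A constant gap of 1 in both arms with a weight-gain difference of 0.5 also gives 0.5/1 = 0.5, with no intervention effect.

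**3. Would an arm term in the planned regressions repair this?** The difference between its coefficients in the two racial/ethnic groups would be an arm-by-race contrast, but one conditional on weight gain, which is measured after randomisation and is the proposed mediator. In the simulation the conditional contrast was about 0 in all three full-mediation scenarios (true values −2, 0, +2). With half-bypass it was about −1, 0 and +1, half the total effect.

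**4. Precision of the missing contrast.** Inputs: SD 3.6 (Sample Size and Power Estimates; measured at discharge, assumed to hold at 3 months); 41% white (Characteristics of participants), with the other 59% counted as minority; 50 infants, or 45 after 10% loss; no twin correlation.

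SE = SD × √(2/(0.59n) + 2/(0.41n)), where n is infants per arm and df = N − 4.

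- N = 45: 3.6 × √(2/13.275 + 2/9.225) = 2.18; half-width 2.02 × 2.18 = 4.4.
- N = 50: 3.6 × √(2/14.75 + 2/10.25) = 2.07; half-width 2.01 × 2.07 = 4.2.
- Power for an illustrative 3-point change in the gap (noncentral t): 27% and 29%.
- SD 3.0 to 5.0 at N = 45: half-width 3.7 to 6.1, power 36% to 16%.
- Black versus white only (56/41): half-width 4.5 and 4.2, power 26% and 29%.
- Change detectable with 80% power at N = 45: about 6.3 points. About 190 evaluable infants would be needed for 3 points.

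Twins are randomised individually. With an assumed 20% to 40% of infants in pairs and within-pair correlation of 0.5 to 0.8, the simulated SE at N = 46 was 2.17 to 2.19, against 2.19 without twins.

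**5. Decomposition run separately by arm.** The gap within one arm has SE 2.18/√2 = 1.54 and a half-width of about 3.2. With 13 minority and 9 white infants, a true gap of 2 and a true share of 1, the central 95% of simulated shares ran from −5.2 to 7.3.

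**The case against.** The strongest reply is that the arm comparison is implied. The Aim 1 overview defines the intervention group by its serial body-composition assessments, so the reference to serial monitoring in the decomposition sentence is close to an arm label. This shows that the authors meant to assess the intervention. It still defines no contrast, and the Intervention paragraph says that control infants are measured serially too, with results withheld from clinicians.

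Second, pooling is not stated, and a by-arm decomposition is equally compatible with the text. That stands: the fault is an undefined comparison, not a demonstrated wrong analysis.

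Third, the illustration varies the control gap so that the pooled gap stays at 1. With the control gap fixed at 2, the same three effects give pooled gaps of 1, 2 and 3. That is true, but the control gap is not known in advance, so a pooled gap alone cannot be read as an effect. The example shows what is possible, not a likely size of error.

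Fourth, part of the method rests on a cited study that cannot be checked here, and a decomposition on weight gain does suit a hypothesis about mechanism. That is a reason to keep it, but not in place of the randomised contrast.

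Finally, this is a secondary aim in a 50-infant pilot, and the plan already expects that "the precision of our estimates and the external validity of our results will be affected by our small sample size". Limited precision argues for estimation over testing. It does not justify leaving the estimand undefined.

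**Conclusion.** The concern holds, confined to the disparity half of Aim 2. Nothing in the plan defines a minority-white gap by arm or an arm-by-race/ethnicity term, and the planned adjustment for demographic characteristics is not an interaction. The regressions and decomposition condition on weight gain after randomisation. If the arms are pooled, they cannot separate interactions of −2, 0 and +2 points under full mediation.

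The contrast that would answer the hypothesis has an expected 95% CI half-width wider than the 3-point difference the plan calls clinically meaningful, across the SD range examined at N = 45. This rests on the assumed 3-month SD and racial/ethnic mix. Aim 2 can therefore be exploratory estimation only. The primary outcome and its sample size are unaffected.

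**What to change.** In the Aim 2 Statistical analysis paragraph:

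- Define the disparity estimand as the arm-by-race/ethnicity interaction on 3-month %BF: the minority-white gap in the intervention arm minus that in control, with a 95% CI.
- Fit the same model to weight gain from discharge to 3 months.
- Do not adjust either model for weight gain after randomisation.
- Label the results exploratory and state the expected CI width.
- Keep the decomposition as a descriptive analysis of the pathway. State whether arms are pooled, which covariates enter, and what observed and predicted differences are compared.
- If the decomposition is also run by arm, warn that the explained share is very unstable at about 13 minority and 9 white infants per arm, and undefined when the gap is near zero.

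The cost is SAP wording and one interaction model on two outcomes already being collected, with no added enrolment or measurement. The drawback is that Aim 2 becomes openly imprecise, and a by-arm decomposition would be close to uninformative.
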